8.1. Institutional Review Board

A copy of the proposed protocol, Informed Consent form, other written patient information and any proposed advertising material must be submitted to the IRB for written approval. A copy of the written IRB approval of the protocol and Informed Consent form must be received by Merck Inc. before recruitment of patients into the Study and shipment of product.

The Investigator must submit and, where necessary, obtain approval from the IRB for all subsequent significant protocol amendments and significant changes to the Informed Consent form. The Investigator should notify the IRB of deviations from the protocol or SAEs.

8.2. Informed Consent form

The written Informed Consent documents should be prepared in the language(s) of the potential patient population.

The IRB must first approve the Informed Consent forms that are used. The Informed Consent forms that are used should be in accordance with the current guidelines as outlined by the Good Clinical Practices (GCP) guidelines, Declaration of Helsinki and the International Conference on Harmonization (ICH).

Prior to participation in the clinical Study, each patient must give written Informed Consent after the context of the study has been fully explained to the patient in language that is easily understood by the patient. The patients must also be given the opportunity to ask questions and have those questions answered to their satisfaction.

Written Informed Consent must be recorded appropriately by means of the patient's, or their legal representative's dated signature. The patient will receive a copy of the Informed Consent form.

8.3. Amending the Protocol

An Investigator may not make protocol changes without prior approval by Merck, Inc. All significant protocol changes that may affect the following must be submitted and approved by the IRB before initiating the change:

- validity of the data or information resulting from the completion of the approved protocol;
- relationship of the likely patient risk to benefit relied upon to approve the protocol;
- scientific soundness of the investigational plan, or;
- rights, safety, or welfare of the human patients involved in the investigation.

8.4. Emergency Actions

Merck, Inc. accepts the right of the Investigator to deviate from the protocol in an emergency and/or break study drug blinding when necessary to safeguard the life or the physical well-being of a study patient. If a patient is displaying signs and/or symptoms of residual neuromuscular blockade that jeopardizes the safety of the patient, the anesthesiologist may decide to administer an additional amount of Sugammadex. In such an event, the patient will remain in the intention to treat group but will be excluded from the analysis between the two treatment groups. The Investigator must give notice of any emergency deviations and justification for the deviation to Merck and the IRB as quickly as possible after the episode, in any event no later than 24 hours after the emergency.

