Several studies have demonstrated decreased morbidity from laparoscopic surgery with the use of deep neuromuscular blockade (DNMB). Using data from laparoscopic colorectal surgery, patients in the DNMB vs. moderate NMB (MNMB) group had IP of 9.3 +/- 1.3 vs. 12.0 +/- 0.5 mmHg group respectively. The DNMB group had lower Numeric Rating Scale (NRS) pain scores [2.3(0.6) to 2.9(0.3)], incidence of shoulder pain (3.3% to 25.8%; a reduction of 87%) Gas Passing Time in hours [40(11.3) to 64(31)] and estimated blood loss (20.2 +/- 13.7 vs 60 +/- 95.3 mL). (Kim, Lee, Lee, Min, & Yoo, 2016) In another study which focused on 99 patients undergoing laparoscopic hysterectomy, 28.6% of the DNMB group (IP 8mmHg) vs. 60% in the MNMB group (IP 12mmHg) experienced shoulder pain. (Madsen, et al., 2016) Robotic surgery may differ from conventional laparoscopic surgery in that the duration of surgery is often more prolonged and the patient may be maintained in different positions (steep Trendelenburg or reverse Trendelenburg), both of which may increase the physiologic effects of pneumoperitoneum.

Sugammadex is a gamma cyclodextrin which directly encapsulates steroid NMB agents such as Vecuronium and Rocuronium thus allowing for safe, rapid and more complete reversal of muscular paralysis. (Flockton, et al., 2008) (Geldner, et al., 2012) With the use of Sugammadex, it is now possible to maintain a continuously deep level of muscular relaxation while also extubating the patient at the end of the operation in a safe and efficient manner. (Carron, Baratto, & Ori, 2016) (Ledowski, et al., 2014) (Duvaldestin, et al., 2010)

The Train of Four (TOF) ratio (or TOFR) is a technique for monitoring the degree of blockade by non-depolarizing neuromuscular blocking agents at the nicotinic acetylcholine receptors (neuromuscular junction). An electrical stimulus is applied by transcutaneous nerve stimulator as a group of four stimuli. The quantity and quality of muscular response to nerve stimulation correlates with the degree of neuromuscular blockade. The number of muscular responses to stimulation (TOF count) of 4, 3, 2 and 1 correlates with approximately 75%, 85%, 90% and 95% neuromuscular blockade. The TOF ratio of T4/T1 is a more objective and sensitive method to quantify the degree of neuromuscular blockade calculated by comparing the strength of muscular response of the last TOF stimuli compared to the first. It was previously thought that a

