4.6. Randomization

Once it has been determined that the patient meets all eligibility criteria, they will be randomized on a 1:1 ratio for Deep Neuromuscular Blockade and Sugammadex or Moderate Neuromuscular Blockade and neostigmine administration. Randomization will be done the morning of surgery by using REDCap randomization tool.

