4.7. Blinding, Allocation and Concealment

Patients and TOF-watch assessors will be blinded to the study drug. The assessor of the primary outcome will not be involved in randomization, or allowed in the operating room during surgery. Anesthesiologists will not be blinded to study drug but he/she will be blinded to the TOF watch response. The surgeon and PACU staff will be blinded to the group assignment.

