4.9. Analysis Plans

Patients' demographic information, laboratory test results and concomitant medications, including neoadjuvant chemotherapy at baseline will be analyzed, with data summarized in tables listing the distributions of the variables along with the number of subjects per treatment arm in order to assess comparability. Patients' information on post-operative shoulder pain, nausea, vomiting, intubation and measures from Postoperative Morbidity Survey will be collected. The Fisher's exact test or Chi-square test will be applied to assess the association between two categorical variables. We will summarize the distribution of average and cumulative intraoperative insufflation pressure, Post Anesthesia discharge DASAIM scores, length of ICU and hospital stay by each treatment. We will use the student t-test or the Wilcoxon rank sum test to compare continuous variables between two different patient groups. Logistic regression will be utilized to assess the effects of patient prognostic factors, comorbidities and treatment on postoperative shoulder pain and postoperative morbidity.

Adverse event (AE) data will be summarized by frequency tables. The association between the types and severity of AE and the treatment will be evaluated.

5. Study Drug Information

Since both Sugammadex and Neostigmine are FDA approved, Insert recommendations and Institutional Standards will be followed for all study agents.

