6.1. Intraoperative Anesthesia Care

All patients will receive a balanced general anesthesia with endotracheal intubation and volatile anesthetic agents. In order to avoid excessive sedation in the PACU, no long acting anesthetic agents (ketamine, dexmedetomidine, etc.) or narcotics (hydromorphone, morphine) will be allowed. Short acting narcotics (fentanyl) are allowed.

Patients will be randomized to receive either the Deep Neuromuscular Blockade (DNMB group) with Sugammadex reversal or Moderate Neuromuscular Blockade (MNMB group) with neostigmine reversal. The patients will be started on a continuous Rocuronium intravenous infusion following intubation. Insert recommendations and Institutional Standards will be used for Rocuronium. For the DNMB group, the rate will be adjusted and boluses given to maintain 1-2 post tetanic responses during the pneumoperitoneum. NMB will be reversed with Sugammadex at the end of surgery. For the MNMB group, the Rocuronium infusion rate will be adjusted to maintain 1-2 TOF responses and will be reversed with neostigmine at the end of surgery. The level of NMB will be assessed by the anesthetist with a standard nerve stimulator at 20 minute intervals for both groups.

During the surgical time-out and at the time of insufflation, the surgeon will be instructed to maintain the lowest insufflation pressure necessary for good surgical exposure and safety throughout the operation. All adjustments to the insufflation pressure will be directed by surgeon.

A clinical coordinator will calibrate the acceleromyography (TOF-Watch® SX, Organon Ireland Ltd., a subsidiary of Merck & Co., Inc., Swords, Co. Dublin, Ireland; pending availability due to product discontinuation by manufacturer) at the adductor pollicis muscle during induction prior to neuromuscular blockade, will record insufflation pressure changes during surgery and acquire the TOF ratio (TOFR) with the TOF-Watch® SX upon arrival of each patient to the PACU. Data will be collected from the electronic medical record (Anesthetic Record, PACU notes, Progress notes, Discharge summary, etc.) as well as a PACU survey.

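### Section 8.4 excludes randomised patients given additional Sugammadex from the between-group analysis, and section 4.9 defines no analysis set

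*Combined protocol and SAP*

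**What the plan says.** Section 8.4 (Emergency Actions) covers patients whose residual neuromuscular blockade threatens their safety. In that case "the anesthesiologist may decide to administer an additional amount of Sugammadex", and "the patient will remain in the intention to treat group but will be excluded from the analysis between the two treatment groups". This is the only mention of intention to treat in the supplied text.

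Section 4.9 (Analysis Plans) lists tests but no population. Categorical variables get Fisher's exact or Chi-square. For the rest, "We will use the student t-test or the Wilcoxon rank sum test to compare continuous variables between two different patient groups". Logistic regression is added for shoulder pain and morbidity. No intention-to-treat, modified or per-protocol set is defined, and none is called primary.

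Three other sections bear on the point:

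- Section 4.6, on timing: "Randomization will be done the morning of surgery by using REDCap randomization tool". Rescue therefore always follows randomisation.
- Section 4.7, on who decides: "Anesthesiologists will not be blinded to study drug but he/she will be blinded to the TOF watch response".
- Section 6.1, on what differs by arm: the deep-block arm is reversed with Sugammadex, and in it "the rate will be adjusted and boluses given to maintain 1-2 post tetanic responses during the pneumoperitoneum". The moderate-block arm is held at a shallower level and reversed with neostigmine.

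**The concern.** Membership of an intention-to-treat group means nothing if the patient is then left out of the comparison between arms. Two analysts could read the same text and choose different primary populations.

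The exclusion is not neutral by design. Residual blockade arises after the assigned block and the assigned reversal agent, and the decision to treat it is made by someone who knows the study drug. The groups left for comparison may no longer be the groups that randomisation created.

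The documents do not show which arm would lose more patients. The Background describes Sugammadex as "allowing for safe, rapid and more complete reversal of muscular paralysis", which suggests more rescue in the neostigmine arm. The deeper block in the other arm, and the reference to an additional amount of Sugammadex, could suggest the opposite.

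Section 8.4 does not limit the exclusion to particular outcomes. It would therefore also apply to DASAIM readiness, pulmonary morbidity and the optional TOF ratio at PACU arrival, where it removes patients selected for poor recovery from blockade.

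**Working it through.** **Inputs from section 4.8.** 48 per group; shoulder pain 60% (control) and 28.6% (deep block); two-sided alpha 0.05; Chi-square test; 88% power; 100 patients enrolled after allowing 4% drop-out.

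**The plan's own figure.** For two proportions, with difference d, pooled standard error s0 and unpooled standard error s1, the probability of rejection is Φ((|d| − 1.96·s0)/s1) + Φ((−|d| − 1.96·s0)/s1).

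- d = 0.600 − 0.286 = 0.314; pooled rate = (0.600 + 0.286)/2 = 0.443.
- s0 = √(0.443 × 0.557 × 2/48) = 0.1014.
- s1 = √(0.60 × 0.40/48 + 0.286 × 0.714/48) = 0.0962.
- Power = 88.5%, which agrees with the stated 88%. Also 96/0.96 = 100. The sample size is not in dispute.

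**Assumptions.** The documents give no rescue rate, no split by arm and no pain rate among rescued patients. All three are assumed over a range. Let p be the arm's true pain rate, r the share rescued and q the pain rate among the rescued. After exclusion the arm shows

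analysed rate = (p − r·q)/(1 − r), with 48(1 − r) patients.

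**No true effect (60% in both arms), rescue in the control arm only**

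| r | q | Analysed control rate | Spurious difference (points) | Two-sided error |
|---|---|---|---|---|
| any of these | 0.60 | 60.0% | 0 | 5.0% |
| 0.02 | 0 | 0.60/0.98 = 61.2% | +1.2 | 5.2% |
| 0.04 | 0 | 0.60/0.96 = 62.5% | +2.5 | 5.7% |
| 0.10 | 0 | 0.60/0.90 = 66.7% | +6.7 | 10.0% |
| 0.10 | 0.30 | 0.57/0.90 = 63.3% | +3.3 | 6.2% |
| 0.10 | 1 | 0.50/0.90 = 55.6% | −4.4 | 7.1% |
| 0.20 | 0 | 0.60/0.80 = 75.0% | +15.0 | 30.8% |
| 0.20 | 0.30 | 0.54/0.80 = 67.5% | +7.5 | 10.9% |
| 0.20 | 1 | 0.40/0.80 = 50.0% | −10.0 | 15.3% |

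A plus sign favours deep block. If rescue is in the deep-block arm only, the error rates are the same and the signs reverse. If both arms have equal rescue and equal pain among the rescued, the error stays at 5%.

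A simulation from 50 per arm agrees. With an average of 5 control patients excluded, the error is 10.4% if none had pain and 7.4% if all did. With 10 excluded it is 32.6% and 16.1%.

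**Planned effect (60% v 28.6%), no pain among the rescued**

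- Deep-block arm only, r = 0.10: 0.286/0.90 = 31.8%; difference 28.2 points; power 78%.
- Deep-block arm only, r = 0.20: 0.286/0.80 = 35.75%; difference 24.3 points; power 61%.
- Control arm only, r = 0.10: 66.7% − 28.6% = 38.1 points.
- Control arm only, r = 0.20: 75.0% − 28.6% = 46.4 points.

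If rescue in the deep-block arm is unrelated to pain (q = 0.286), the difference stays at 31.4 points. Power is then 86.6% at r = 0.10 and 84.4% at r = 0.20. Lost numbers alone cost little; the damage comes from selection.

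**The case against.** The strongest reply is that keeping a patient in the intention-to-treat group makes sense only if an intention-to-treat comparison exists. On that reading the excluded comparison is a loosely worded per-protocol one, and nobody leaves the main result. That may be what was meant. But no section of the supplied text plans such a comparison, and 8.4 refers to the restricted one as though it were the only comparison between arms.

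The trigger is also narrow. It requires a threat to the patient's safety, and the emergency deviation must be notified to the sponsor and the IRB within 24 hours. Rescue may therefore be rare, and at 2% to 4% the error barely moves even with no pain among the rescued. This stands, and it limits the likely size.

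The large figures stack assumptions: high rescue, all in one arm, and a strong link to pain. The Background attributes shoulder pain to carbon dioxide irritating the diaphragm, and no mechanism ties it to residual blockade. This also stands. The q = 0 and q = 1 rows are bounds, not forecasts.

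On recovery outcomes, a patient rescued before PACU arrival may score normally there, so the exclusion need not shift every such measure. That is why the timing of rescue has to be reported.

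None of these points supplies the missing definition of the primary population.

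**Conclusion.** The concern holds. As written, the plan removes randomised patients from the treatment comparison because of a post-randomisation event that depends on assigned treatment and is judged by an anesthesiologist who knows the study drug. No section defines a population that would restore them.

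The numerical effect on shoulder pain cannot be fixed from the documents. It is nil if rescue is unrelated to pain, and small at rescue rates of a few per cent. It becomes material at 10% to 20% only if rescue is unbalanced between arms and related to pain, and its direction is unknown. The contradiction between 8.4 and 4.9 exists at any rescue rate. It should be settled before the data are seen.

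**What to change.** - **Section 8.4:** delete the exclusion from the between-group analysis. The provision for giving additional Sugammadex is left as it is.
- **Section 4.9:** state that all randomised patients are analysed in their assigned arm for the primary and secondary outcomes, whether or not they received additional Sugammadex. Since 4.8 allows for 4% drop-out, the same paragraph should say how a patient with no PACU pain record is handled.
- **Reporting:** give the number rescued in each arm and whether rescue came before or after PACU arrival, because recovery measures taken after rescue will not by themselves show the event.
- **Sensitivity analysis:** an analysis without rescued patients may be kept if it is labelled as such.

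The cost is one sentence in 8.4 and a few in 4.9, through a protocol amendment, with no extra patients. The downside is that the estimate may be slightly diluted relative to a per-protocol effect.

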TOFR greater than 0.7 indicated sufficient neuromuscular recovery for extubation. Evidence now suggests that one can have an increased risk of upper airway obstruction and aspiration due to residual neuromuscular blockade with a TOFR less than 0.9, though more prospective studies are needed.

Elderly patients compared to the general population may receive more benefit from the reversal of NMB with Sugammadex as opposed to neostigmine but more prospective studies are needed. In a large retrospective study of 1444 patients, those who had an age greater than 60 and an ASA score of 3 or 4 had a small but significantly higher incidence of postoperative pulmonary complications when treated with neostigmine compared to Sugammadex. (Ledowski, et al., 2014) Additional investigation may identify subgroups within the elderly population who are the highest risk for complications of elevated insufflation pressures or residual neuromuscular blockade.

While there is no universal age which defines the elderly, we chose the age of 65 years or greater to be our threshold based on the Phase 3 trial which demonstrated the safety and efficacy of Sugammadex in the elderly population. Overall, 150 patients were treated and had at least one post-baseline efficacy assessment; 48 were aged 18-64 yr (adult), 62 were aged 65-74 yr (elderly), and 40 were aged 75 yr or older (old-elderly). The geometric mean time (95% confidence interval) from Sugammadex administration to recovery of the TOF ratio to 0.9 increased with age, from 2.3 (2.0-2.6) min (adults) to 2.9 (2.7-3.2) min (elderly/old-elderly groups combined). Recovery of the TOF ratio to 0.9 was estimated to be 0.7 min faster in adults compared with patients aged 65 yr or older ($P = 0.022$). Sugammadex was well tolerated by all patients. (McDonagh DL, 2011)

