4.8. Sample Size Justifications

For 99 patients undergoing laparoscopic hysterectomy, 28.6% of the DNMB group (IP 8mmHg) vs. 60% in the MNMB group (IP 12mmHg) experienced shoulder pain. (Madsen, et al., 2016)

Using the data from the aforementioned study, a sample size of 48 per group will enable the study 88% power to detect the decrease in the rate of postoperative shoulder pain from 60% for the control group to 28.6% for the group with deep Neuromuscular Blockade and Sugammadex, assuming a two-sided type I error rate of 0.05 using a two-group Chi-square test (nQuery Advisor 7.0). Postoperative shoulder pain is defined as any shoulder pain recorded before the discharge from PACU. We predict that the typically increased length of robotic surgery in combination with potentially lower insufflation pressures (6-7mmHg) may result in an even greater difference between the two groups. We want to factor in a 4% drop-out rate, therefore, we will enroll a total of 100 patients.

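### Section 8.4 keeps a rescued patient in the intention-to-treat group by name but drops that patient from the between-group comparison, and no other analysis set is defined

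*Combined protocol and SAP*

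**What the plan says.** Section 8.4 (Emergency Actions) sets the trigger: "If a patient is displaying signs and/or symptoms of residual neuromuscular blockade that jeopardizes the safety of the patient". In that case the anesthesiologist may choose to give more Sugammadex. The consequence for the analysis is that "the patient will remain in the intention to treat group but will be excluded from the analysis between the two treatment groups". Nowhere else does the document mention intention to treat.

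Section 4.9 (Analysis Plans) covers the primary outcome with a general statement that Fisher's exact test or the "Chi-square test will be applied to assess the association between two categorical variables". It defines no intention-to-treat set, no per-protocol set and no sensitivity analysis.

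Three other places bear on the point:

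- **Treatment.** Sections 4.6 and 6.1 make the reversal drug part of the randomized strategy: deep block with Sugammadex, or moderate block with neostigmine.
- **Blinding.** Section 4.7 states: "Anesthesiologists will not be blinded to study drug but he/she will be blinded to the TOF watch response". The person who decides on rescue therefore knows the arm.
- **Sample size.** Section 4.8 plans 48 per group and adds: "We want to factor in a 4% drop-out rate, therefore, we will enroll a total of 100 patients". It also defines the primary outcome as any shoulder pain recorded before PACU discharge.

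**The concern.** Randomization protects the comparison only if patients are counted in the arm to which they were assigned, whatever happens later. The rule in 8.4 removes patients for something that happens after randomization and may be affected by treatment. Residual block depends on how well the block was reversed, and the Background says that Sugammadex encapsulates the blocking drug, "thus allowing for safe, rapid and more complete reversal of muscular paralysis". Rescue could therefore be more frequent in one arm. The decision is also discretionary and made by an unblinded clinician.

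If rescued patients differ from the others in shoulder pain, dropping them changes the estimated difference for reasons unrelated to the treatment effect. Even if they do not differ, the sentence leaves the primary dataset undetermined. One analyst would keep rescued patients because they belong to the intention-to-treat group. Another would drop them because the text says so. That choice could be made after the data are seen.

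**Working it through.** **Inputs (section 4.8).** Control rate 60%, deep-block rate 28.6%, 48 per group, two-sided alpha 0.05, two-group chi-square test, stated power 88%, 100 enrolled. With 1:1 allocation (section 4.6), 100 enrolled is 50 per arm. The number excluded, k, is an assumption, since the documents give no rescue rate.

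**1. The plan's own figure.** Power = Φ[(|p1 − p2| − 1.96 × SE0) / SE1], where SE0 uses the pooled rate and SE1 the separate rates.

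- Pooled rate = (0.60 + 0.286)/2 = 0.443.
- SE0 = √(0.443 × 0.557 × 2/48) = 0.1014.
- SE1 = √(0.60 × 0.40/48 + 0.286 × 0.714/48) = 0.0962.
- Power = Φ[(0.314 − 0.1987)/0.0962] = 88.5%.

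This agrees with the stated 88%. Four losses (4% of 100) leave 96, or 48 per group. The sample size itself is not in dispute.

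**2. How far the estimate can move.** Keep the full-arm rates at the planned values and remove k = 2 patients from one arm. The extremes are that both had shoulder pain or that neither did.

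| Arm losing 2 of 48 | Expected events, full arm | Retained rate if both had pain | Retained rate if neither had | Difference (full-arm value 31.4) |
|---|---|---|---|---|
| Control | 0.60 × 48 = 28.8 | 26.8/46 = 58.3% | 28.8/46 = 62.6% | 29.7 to 34.0 points |
| Deep block | 0.286 × 48 = 13.7 | 11.7/46 = 25.5% | 13.7/46 = 29.8% | 34.5 to 30.2 points |

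These are outer limits. With milder assumed pain rates of 30% or 90% in two excluded controls, the difference is (28.8 − 0.6)/46 − 28.6% = 32.7 points, or (28.8 − 1.8)/46 − 28.6% = 30.1 points. If the excluded controls have pain at the control-arm rate of 60%, there is no bias.

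**3. Loss of numbers alone.** Use the same power formula with unequal groups and unchanged rates.

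- 46 controls and 48 deep block: 87.8%.
- From the 100 enrolled with no other losses, 48 controls and 50 deep block: 89.1%.
- Likewise 45 controls and 50 deep block: 88.1%.

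Excluding five controls from a fully retained sample still meets the planned 88%. Reduced numbers are not the issue.

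**The case against.** **The sentence may describe two analyses.** It could mean that an intention-to-treat analysis keeps the patient and a second comparison leaves the patient out. That would be good practice. But section 4.9 describes no second analysis, and 8.4 does not say which of the two would be primary. If this was the intention, the fix below puts it in writing.

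**Rescue is likely to be rare and unrelated to shoulder pain.** The trigger is a threat to safety. The Background attributes shoulder pain to carbon dioxide irritating the diaphragm, which happens before reversal. This stands, and it limits the size of the concern. A reader might infer a large bias by supposing that a fifth of controls are rescued. Nothing in the documents supports such a rate.

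**The direction is not known.** A reader might infer that only neostigmine patients would be excluded and that the result would tilt toward deep block. The Background makes unequal rescue plausible, but 8.4 speaks of an additional amount of Sugammadex, and that wording fits patients who have already received it. Either arm could be affected, and the estimate could move either way.

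**A reader might also infer a safety gap,** because section 4.7 gives no end to the anesthesiologist's TOF-Watch blind and no rule requires a low PACU ratio to be reported. The documents do not establish a defect here. The reading is optional and exploratory (4.3.1) and depends on a discontinued device (6.1). Rescue on signs or symptoms stays open under 8.4. PACU staff score sedation, obstructed breathing and oxygen saturation at 15, 45 and 90 minutes if the patient is still there (6.2.5). A mandatory report could also prompt a visible rescue that hints at the arm to the blinded nurse who records shoulder pain. That is a trade-off for the investigators.

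**Conclusion.** The rule in 8.4 contradicts itself and, followed literally, departs from intention to treat in the between-group comparison. That conclusion rests on the text and needs no assumption about rates. Its numerical effect is unknown and may be nil. With two exclusions in one arm, an assumed figure, the difference stays within 29.7 to 34.0 points for controls or 30.2 to 34.5 for deep block, against a planned 31.4. Loss of power is negligible. The point deserves correction because the rule governs who is counted in the primary comparison, the decision to rescue is unblinded, and the remedy costs almost nothing. It is not evidence that the trial's result would be materially biased.

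**What to change.** In 8.4 and 4.9, state that all randomized patients with outcome data are analyzed in their assigned group for the primary comparison, whether or not additional Sugammadex was given. Report the number rescued in each arm. If a comparison without rescued patients is wanted, define it in 4.9 as a sensitivity analysis and label it so.

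The cost is a short amendment. No new data collection is needed: 8.4 already requires emergency deviations to be notified within 24 hours, and 8.5 puts patient-specific deviations on a case report form. Shoulder pain before PACU discharge can be recorded for rescued patients like any others. The one downside is interpretive: the estimate then describes each strategy including any rescue, not the effect that would be seen if no one needed it.
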